13.2.2. Missing Data Methods for Secondary Efficacy Variable(s)

Missing data will be imputed using the control-based imputation described in section 13.1.3 for BCVA measured in LogMAR,

Total score and individual subscale scores form the VFQ-25, composite score and individual domain score as well as categorical secondary efficacy endpoints will not be imputed.

13.2.3. Analysis of Secondary Efficacy Variables

Change in LogMAR BCVA analysis

Change in LogMAR compared to baseline, at each timepoint of the Follow-Up Period up to 5 years post- treatment will be analyzed at each visit using separate ANCOVA models as primary endpoint (see section 13.1.4).

Response status

For each response parameter and at each timepoint of the Follow-Up Period up to 5 years post- treatment, logistic model, including a factor for treatment group and the baseline value as a covariate will be considered on:

- Second-affected eye at timepoint (at eye level)
- First-affected eye at timepoint (at eye level)
- First and second affected eye at timepoint (at subject level): best response between both eyes

SAS code:

```
ARM=subject Treatment arm (1=GS010 – 0=Placebo); resp=responder variable; Logmar0=Logmar at baseline;
proc logistic data=XXX;
class ARM;
model resp=logmar0 ARM;
run;
```

For each of the response definitions and at each timepoint of the Follow-Up Period up to 5 years post- treatment, a logistic model, including a factor for treatment group, eye, the baseline value as a covariate, will be fit using GLMM for first and second affected eye at timepoint (at eye level)

SAS code:

```
ARM=subject Treatment arm (1=GS010 – 0=Placebo); resp=responder variable; Logmar0=Logmar at baseline;
proc glimmix data=XXX_ana;
class ID ARM;
model resp= ARM logmar0 /dist=bin solution cl;
random intercept/sub=ID type=ar(1);
run;
```

Parameters measured with SD-OCT, HVF and contrast sensitivity

The parameters detailed in sections 13.2.1 will be analyzed separately using a MMRM model, with adjustment for baseline score, as described in section 13.1.6.

Quality of Life assessments

Visual Functioning Questionnaire-25 (VFQ-25)

VFQ25 measures will be assessed at the subject level, looking at change from baseline for all subjects and comparing the change from baseline between the two arms (bilaterally treated subjects vs. unilaterally treated subjects).

Composite score and individual subscale scores from VFQ-25 will be summarized using descriptive statistics. Change from baseline at each visit for the composite score and individual subscales scores will be analyzed separately using a MMRM model, with adjustment for baseline score, as described in section 13.1.6.

36-Item Short Form Health Survey, Version 2 (SF-36v2)

SF-36 measures will be assessed at the subject level, looking at change from baseline for all subjects and comparing the change from baseline between the two arms (bilaterally treated subjects vs. unilaterally treated subjects).

Composite scores and individual domains from SF-36v2 will be summarized using descriptive statistics. Change from baseline at each visit for the composite scores and individual domains will be analyzed separately using a MMRM model, with adjustment for baseline score, as described in section 13.1.6.

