LHON manifests as acute to sub-acute, sequential, bilateral, painless vision loss. It is a bilateral disease and clinical manifestation is essentially predictive of bilateral involvement. Greater than 97% of subjects are reported to have bilateral involvement at 12 months and occurrences of unilateral involvement in retrospective reports of cohorts with LHON are very rare (Newman 1991, Riordan-Eva 1995). Lam et al. (Lam 2014) reported a G11778A *ND4* cohort in which 53% reported bilateral involvement in  $\leq 2$  months and 80% reported bilateral involvement in  $\leq 6$  months.

The clinical hallmark of LHON is central vision loss (Sadun 2011). This is accompanied by dysfunction of color and contrast vision and central and cecocentral visual field defects. Newman et al. (Newman 1991) reported a final visual acuity of 20/200 or worse in 98% of eyes. Lam et al. (Lam 2010, Lam 2014) performed a prospective natural history study of LHON subjects with the G11778A *ND4* mutation. The primary outcome was the finding of no significant difference in

ETDRS visual acuity at 12, 24 or 36 months of follow-up compared to baseline at study entry. This finding was for the entire cohort as well as for the subgroups of subjects who entered the study within 12 months of disease onset or after 12 months of disease onset. 14.7% of total study eyes, in 18% of study subjects, had improvement by  $\geq 15$  ETDRS letters over the study period. Eighty-six percent of subjects had eyes with stable acuities during study follow-up. Subjects entering the study after 36 months from disease onset showed no change or improvement of visual acuity over follow-up. The authors concluded that for G11778A *ND4* mutation spontaneous natural recovery is partial and occurs on a very limited basis in a small percentage of subjects and thus gene therapy interventions can be measured for efficacy with a reasonable sample size.

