### 16.2 Sample Size

Sample size calculation is based on the primary endpoint which is the change from baseline to 1.5 years post-treatment of the visual acuity (LogMAR). Masked preliminary data of the Phase III RESCUE and REVERSE sham-controlled studies of GS010 and monitored data from the Phase I/IIa safety and tolerability study of GS010 are used to estimate the standard deviation of the change from baseline to each available visit. These data do not take into account a potential treatment effect in the RESCUE and REVERSE studies and if there is an effect the standard deviation may be over-estimated.

From this masked preliminary analysis, a SD of 0.55 LogMAR has been estimated for the LogMAR change from baseline; this is reduced to 0.50 with the inclusion of baseline LogMAR as a covariate. Using this reduced value for SD and a treatment effect of 0.3 LogMAR in the change from baseline, the requested sample size to reach a power of 80% ( $\alpha = 0.05$  two-sided) according to an ANCOVA model including the baseline LogMAR value as covariate has been estimated, using SAS PROC POWER, to be 45 evaluable subjects per treatment group (i.e. 90 subjects in total).

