#### *16.4.1.10 Primary Significance Level*

The analysis will be performed using a significance level of 0.05 (two-sided).

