13.2.1. Secondary efficacy variables & derivations

Change in LogMAR BCVA

The first secondary efficacy endpoint is the change from baseline in LogMAR BCVA to each follow-up visit (after 1.5 years) (see section 13.1.4) with the same missing data imputation strategy.

For 5-year analysis, additional supportive analyses will be done:

- Using last available LogMAR value
- Same analysis on PP5Y population.

Response status

The second secondary efficacy endpoint is the responder rate.

For subjects discontinued prior to the time of analysis or with missing data, LOCF imputed data will be used.

Three definitions of responders are given below:

Definition 1 – Gainer eyes:

Eyes whose LogMAR BCVA improves (i.e. decrease) by ≥ 0.3 LogMAR (equivalent to a gain of ≥ 15 ETDRS letters) compared to baseline, i.e. an eye is a responder if: $\text{LogMAR at interest timepoint} - \text{LogMAR at Baseline} \leq -0.30$.

Definition 2 – Stabilized eyes:

Eyes whose LogMAR BCVA does not worsen (i.e. does not increase) by ≥ 0.3 LogMAR (equivalent to an eye that loses ≤ 15 ETDRS letters) compared to baseline, i.e. an eye is a responder if: $\text{LogMAR at interest timepoint} - \text{LogMAR at Baseline} \leq 0.30$.

Definition 3 - Not legally blind:

Eyes whose LogMAR visual acuity is < 1.0 at interest timepoint (i.e. better than LogMAR 1.0, equivalent to better than Snellen acuity of 20/200).

This third definition of interest is exploratory given the precipitous vision loss experienced by the majority of ND4 LHON subjects. Any significant difference in the percentage of second-affected/not-yet-affected responder eyes, receiving GS010 compared to placebo, is pertinent considering the seriousness of the visual impairment.

The response status will be assessed at eye and subject level.

For subject response, the best response observed in either eye will be considered (LogMAR measured on both eyes will not be considered).

Parameters measured with SD-OCT

The changes from baseline at each time point in the following parameters as measured by the SD-OCT:

- Total and Temporal Quadrant Retinal Nerve Fiber Layer (RNFL) thickness;
- Papillo Macular Bundle (PMB) RNFL thickness
- Ganglion Cell Layer macular volume
- ETDRS macular volume

HVF 30-2

The changes from baseline at each time point the following parameters of standardized, automated visual fields obtained with the HVF Analyzer II (HVF 30-2):

- Mean deviation
- Foveal threshold sensitivity
- Pattern standard deviation

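### The responder models have no method for sparse or empty cells; if placebo responders are rare, the exploratory LogMAR < 1.0 comparison can lose its odds ratio and much of its power

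*SAP*

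**What the plan says.** SAP 13.2.3 (Response status) applies one approach to all responder definitions at all visits up to Year 5: a "logistic model, including a factor for treatment group and the baseline value as a covariate will be considered on" the second-affected eye, the first-affected eye, and the better response of the two at subject level. The model statement is "model resp=logmar0 ARM", with no options. The SAP names neither the test nor the type of interval. A mixed logistic model for both eyes together is added.

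Definition 3 in SAP 13.2.1 is "Eyes whose LogMAR visual acuity is < 1.0 at interest timepoint". It is labelled exploratory, but the same section treats any significant difference on it as pertinent. SAP 13.3 sends further endpoints through the same models, including LogMAR ≤ 1.0 and < 1.0.

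The only fallback for a failing model is in SAP 6.5, which changes the covariance structure of mixed models. SAP 6.3 gives all of the type I error to the primary endpoint. Protocol 16.4.2.1 judges the clinical relevance of each responder comparison by an odds ratio below 0.8.

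No document gives an expected placebo rate for definition 3. The nearest figure is in Protocol 6.1, where a historical series "reported a final visual acuity of 20/200 or worse in 98% of eyes".

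**The concern.** When one arm has no responder, the maximum-likelihood odds ratio is infinite. Its Wald standard error grows faster than the estimate, so the Wald p-value drifts towards 1 and depends on where the iterations stop. Swapping covariance structures cannot repair this, and the logistic model has none to swap.

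The historical figure implies that about 2% of eyes end better than 20/200, so an empty placebo arm is a foreseeable outcome for definition 3. The protocol wants an odds ratio for this endpoint, and there would be none to report. The analyst would then publish an uninformative result or choose another method with the unmasked data in view.

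**Working it through.** **1. The plan's own figure.** Protocol 16.2 uses a difference of 0.3 LogMAR, an SD of 0.50, two-sided alpha 0.05 and 80% power.

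n per arm = 2 × (1.960 + 0.842)² × 0.50² / 0.30² = 43.6, so 44 by the normal approximation. The t-based calculation gives 44.6, so 45. The stated 45 per arm is reproduced. It concerns the primary endpoint only; the documents give no rate or power for any responder endpoint.

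**2. Chance of no placebo responder.** P(0 of 45) = (1 − p)^45.

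| Placebo rate p (assumed) | Expected of 45 | P(none) |
|---|---|---|
| 2% (100% − 98%, Protocol 6.1) | 0.9 | 0.98^45 = 40.3% |
| 3% | 1.35 | 25.4% |
| 5% | 2.25 | 9.9% |
| 10% | 4.5 | 0.9% |
| 14.7% (natural-history gain of ≥ 15 letters, Protocol 6.1; bears on definition 1) | 6.6 | 0.08% |

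Adding baseline LogMAR as a covariate barely changes this. Under an assumed baseline distribution, with 2% on placebo and 15 to 20% on GS010, 39 to 40% of simulated trials had no finite estimate.

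**3. One table: 0/45 placebo v 7/45 GS010.**

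- Maximum likelihood with a Wald test: after 8 iterations log OR 7.51, SE 14.9, z = 0.50, p = 0.61; after 12 iterations log OR 11.51, SE 109.7, p = 0.92.
- Likelihood-ratio test on the same model: p = 0.001.
- Fisher's exact test: p = 0.012.
- Firth: in an unadjusted 2 × 2 table this equals adding 0.5 to each cell, so OR = (7.5/38.5)/(0.5/45.5) = 17.7. The penalised likelihood-ratio p is 0.005. A Wald test on the Firth fit gives p = 0.054, so the estimator alone is not enough.

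**4. Power.** Exact enumeration of two binomials, 45 per arm, unadjusted, two-sided 0.05, with empty-arm tables counted as Wald non-rejections. All rates are assumptions.

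| Placebo v GS010 | Empty arm | Wald | Firth (penalised LR) |
|---|---|---|---|
| 2% v 15% | 40% | 18% | 63% |
| 2% v 20% | 40% | 38% | 84% |
| 3% v 20% | 25% | 43% | 76% |
| 5% v 20% | 10% | 43% | 59% |
| 10% v 25% | 1% | 44% | 46% |
| 10% v 30% | 1% | 65% | 67% |

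With equal rates in both arms, Firth rejects in 1.0%, 4.1%, 4.6%, 4.6% and 4.9% of trials at 2%, 5%, 10%, 15% and 30%, so it stays within 5%.

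**5. Both events together.** The chance that a trial has no finite odds ratio and also shows a Fisher-significant GS010 advantage, at a 2% placebo rate, is 11.8%, 27.6%, 36.7% and 39.6% for GS010 rates of 10%, 15%, 20% and 25%. At 5% v 20% it is 9%.

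**The case against.** A reader might infer that the trial expects about one responder in 45 placebo eyes, and that 40% of trials would therefore turn a clear GS010 advantage into a non-significant result. The documents do not support that, for three reasons.

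- **The 2% is not this trial's rate.** It is final acuity in a historical series. Here the primary eye may be not yet affected (Protocol 9.1), vision loss may be of any extent (Protocol 10.2.1), and the primary timepoint is 1.5 years. Every placebo-arm subject also has GS010 in the fellow eye, and Protocol 6.2.1 reports a 12-letter gain in REVERSE sham eyes at Week 72. Rates above 2% are plausible, and by 10% the problem has almost gone.
- **No finite odds ratio and a lost significant result are different events.** Step 5 puts them together at 12 to 40% of trials even at 2%, depending on the GS010 rate.
- **Non-significance belongs to the Wald test.** That is the software default and not something the SAP states; the likelihood-ratio test on the same fit is clearly significant.

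It is also fair to say that definition 3 is exploratory and outside alpha control, and that counts and percentages would show 0/45 v 7/45 plainly. The sparse-placebo argument does not reach first-affected eyes, which receive GS010 in both arms, or subject-level best response, which always includes a GS010 eye.

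These points limit the scope and size. They do not supply the missing method: the test is unnamed, no rule covers an empty cell, and at 5% v 20% the Wald test still gives up 59 − 43 = 16 points of power.

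**Conclusion.** The gap is real but narrow. SAP 13.2.3 prescribes ordinary maximum likelihood for every responder endpoint and gives no method for sparse data. The practical exposure is definition 3 and its SAP 13.3 variants in second-affected eyes. Its size depends on a placebo rate that the documents do not state: it is serious at 2 to 3%, moderate at 5% and negligible at 10%. The power comparison assumes 45 eyes per arm, no covariate, and the default Wald test. Definition 1 is essentially untouched at its natural-history rate, and the primary analysis is not involved. This is a low-cost improvement to an exploratory endpoint, worth making because the SAP attaches meaning to a significant difference there and the protocol reads the result as an odds ratio.

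**What to change.** In SAP 13.2.3, before unmasked results are seen, specify Firth penalised likelihood for the PROC LOGISTIC responder models, with profile penalised-likelihood intervals: `model resp(event='1') = logmar0 ARM / firth clparm=pl clodds=pl;`. State that the p-value is the penalised likelihood-ratio p-value and not the one in the default Wald table; step 3 shows that the choice can decide significance.

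The minimum scope is definition 3 and its SAP 13.3 variants in second-affected eyes, at all visits and whatever the counts, so that the method does not depend on the data. Using it for all definitions is also acceptable, because results are nearly identical when responders are common. SAP 3.6 unmasks at 1.5 years while these models run to Year 5. For any visit whose unmasked results have already been seen, label the Firth result as added afterwards and show it beside the planned output.

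The cost is one model option and a sentence or two in the SAP. Odds ratios shrink slightly, and the test is mildly conservative at very low rates (1.0% rejection when both arms are at 2%).

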#### *LogMAR:*

Three definitions of responders for LogMAR are given in Section 8.2 where the first definition is the most important. The first responder definition (Gainer eyes) is an eye whose LogMAR BCVA improves (i.e. decreases) by  $\geq 0.3$  LogMAR:

LogMAR at 1-5 years – LogMAR at Baseline  $\leq -0.30$  = responder eye.

A logistic regression, with adjustment for baseline, will be performed to compare differences in responder rates. An odd ratio less than 0.8 between treatment groups will be considered as a clear clinically pertinent effect. An interaction with region will be assessed. The second definition of responder (“Stabilized eyes”) is an eye whose LogMAR BCVA does not worsen (i.e. does not increase) by  $\geq +0.3$  LogMAR:

LogMAR at 1.5 Years – LogMAR at Baseline  $\leq +0.30$  = responder eye.

The third definition of interest is exploratory given the precipitous vision loss experienced by the majority of ND4 LHON subjects. The third definition of responder eye is an eye whose LogMAR visual acuity is better (i.e. lower) than 1.0 (i.e. equivalent to being better than a Snellen acuity of 20/200). Any significant difference in the percentage of second affected/not yet affected responder eyes, receiving GS010 compared to placebo, is pertinent considering the seriousness of the visual impairment. The same analysis as for the first responder definition will be performed for the second and third definitions of responder.

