Subjects meeting all eligibility criteria for selection and inclusion will be randomized to treatment arm 1 (TARM1) or treatment arm 2 (TARM2) in a 1:1 allocation (see Figure 1). Subjects in TARM1 will receive intravitreal GS010 in their first affected eye and their second-affected/not-yet-affected eye. Subjects in TARM2 will receive intravitreal GS010 in their first affected eye and placebo intravitreal injection in their second- affected/not-yet-affected eye. For subjects who report simultaneous onset of vision loss in both eyes, the right or left eye will be selected randomly to serve as the second-affected/not-yet-affected eye.

If the right eye is selected randomly as the second-affected/not-yet-affected eye, the left eye will be designated as the first affected eye, and vice versa.

Figure 1: Study Treatment Arms; Post-Treatment Follow-up Period 1: up to 2 years post-treatment

Administration of an Intra ocular pressure (IOP) lowering agent of the investigator's choice will precede all intravitreal injections. Pre-intravitreal injection procedural preparation will include pupil dilation, topical antisepsis, and topical anesthesia. The IMPs (GS010 and placebo) will be administered with a standard intravitreal injection procedure. Each eye will undergo administration of the allocated treatment with a single intravitreal injection, performed as a separate procedure. Please refer to the Intravitreal GS010/Placebo Injection Guide for full details.

Per the Investigator's discretion and according to local standard accepted medical practices, treatment administration to both eyes may be performed at a single Treatment Visit (Visit 3) (i.e. intravitreal injection of both eyes of a given subject is performed the same day as two separate procedures) or may be performed on two consecutive days (i.e. one eye of the subject will be administered the allocated treatment one day and the next day the fellow eye of the subject will be administered the allocated treatment).

Inclusion Visit (Visit 2) vision test results will serve as the baseline values for both eyes of a given subject when the treatments are administered on the same day and when they are administered on consecutive days. Study Day 0 is the day that treatment administration is completed to both eyes; in the setting of treatment administration on consecutive days, this will be the second treatment day. The timing of visits and visit

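### The pooled two-eye responder model codes GS010-treated first eyes of TARM2 as placebo, which pulls its odds ratio toward 1 if it is read as GS010 versus placebo eyes

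*SAP*

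**What the plan says.** **Models.** SAP 13.2.3 (Response status) first gives three separate logistic models: second affected eye, first affected eye, and the subject's better eye. All are coded "model resp=logmar0 ARM". It then adds an eye-level model for both eyes together, "including a factor for treatment group, eye, the baseline value as a covariate, will be fit using GLMM". The code for that model is "model resp= ARM logmar0 /dist=bin solution cl" with a random intercept per subject, and its treatment variable is "ARM=subject Treatment arm (1=GS010 – 0=Placebo".

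**Treatment of the eyes.** SAP 3.1: "Subjects in TARM2 will receive intravitreal GS010 in their first affected eye", with placebo only in the second eye.

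**Coding elsewhere.** SAP 13.1.5 uses a four-level per-eye variable, `TREAT`, which keeps TARM2 first eyes as a GS010 group. Protocol 16.4.2.1 also groups eyes by what the eye received.

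**Reach.** SAP 13.3 sends clinically relevant recovery and its other responder endpoints to 13.2.3.

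**Stabilised eyes.** SAP 13.2.1 Definition 2 covers an eye that "does not worsen (i.e. does not increase) by ≥ 0.3 LogMAR". It equates this with losing no more than 15 letters, and its formula accepts a change of at most 0.30. Protocol 8.2 and 16.4.2 repeat the words and the letters; Protocol 16.4.2.1 pairs the words with the formula. SAP 13.1.1 fixes count fingers (CF) at 2.0 and hand motion (HM) at 2.3.

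**Odds-ratio criterion.** Protocol 16.4.2.1: "An odd ratio less than 0.8 between treatment groups will be considered as a clear clinically pertinent effect". The SAP does not carry this criterion, and SAP 3.4 does not list its removal.

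**The concern.** Secondary objective 3 asks for GS010 versus placebo responder rates in second affected eyes. A reader of the pooled output will see a coefficient labelled GS010 versus placebo and take it as the effect of treating an eye. It is not: it averages a randomised drug contrast in second eyes with a comparison of GS010 against GS010 in first eyes. The result understates any drug effect, and the same model is repeated over several definitions and visits.

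Two further ambiguities affect how the results are counted and judged. An eye that worsens by exactly 0.30 is stable or not stable depending on which part of the definition is programmed. An odds ratio below 0.8 means benefit or harm depending on an orientation that is not stated.

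**Working it through.** **1. The plan's own figure.** The responder analyses have no power calculation. The only one in the documents is 45 per group for the primary endpoint (difference 0.3, SD 0.50, two-sided alpha 0.05, power 80%). It reproduces: the noncentral t gives power 0.795 at 44 and 0.804 at 45 per group. Nothing below changes it.

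**2. Share of mislabelled eyes.** Each TARM2 subject contributes one placebo eye and one GS010 eye. With 45 subjects, 90 eyes enter as `ARM`=0 and 45 of them (50%) received GS010.

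**3. Dilution in closed form.** Let p0 be the placebo-eye response rate and p1 the GS010-eye rate under a true per-eye odds ratio. Assume the GS010 rate is the same in first and second eyes. The model then compares odds(p1) with odds((p0+p1)/2). The 14.7% is the natural-history rate in Protocol 6.1; 25% and 40% are assumptions.

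Worked case, p0 = 0.147 and true odds ratio 2:
- placebo odds = 0.147/0.853 = 0.1723
- GS010 odds = 0.3447, so p1 = 0.256
- pooled `ARM`=0 rate = (0.147+0.256)/2 = 0.202, odds 0.2526
- odds ratio = 0.3447/0.2526 = 1.36

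| True odds ratio | p0 = 14.7% | p0 = 25% | p0 = 40% |
|---|---|---|---|
| 1.5 | 1.21 | 1.21 | 1.22 |
| 2 | 1.36 | 1.39 | 1.41 |
| 3 | 1.60 | 1.67 | 1.75 |

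Between 43% and 51% of the log odds ratio survives. Equal GS010 rates in the two eyes are not essential. Take assumed second-eye rates of 35% versus 20% (odds ratio 2.15) and first eyes at 30% in both arms. The pooled rates are 32.5% and 25%, and (0.325/0.675)/(0.25/0.75) = 1.44.

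**4. The mixed model itself.** A random-intercept logistic model was fitted to 20,000 simulated subjects. The settings were intercept -1.5, random-intercept SD 0.5, 1 and 2, no baseline covariate and no eye effect other than treatment.

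| Model | True odds ratio 2 | True odds ratio 3 |
|---|---|---|
| `ARM` only, as coded | 1.34–1.48 | 1.57–1.63 |
| `ARM` + eye main effect, as in the text | 1.35–1.49 | 1.59–1.65 |
| Per-eye treatment + eye | 1.95–2.22 | 2.90–3.05 |

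Restoring the missing eye term therefore does not help; coding treatment per eye does.

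**5. Stabilised boundary.** 15 letters × 0.02 = 0.30, and CF to HM is 2.3 − 2.0 = 0.30. Every CF-to-HM change falls exactly on the boundary, where the words say not stable and the formula and the letters say stable. Rounding matters too. In double precision 2.3 − 2.0 evaluates to 0.2999999999999998, so the unrounded change is also not ≥ 0.3. Likewise 2.0 − 2.3 evaluates to −0.2999999999999998 and fails ≤ −0.30, so unrounded code would drop HM-to-CF gainers under Definition 1.

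**6. Odds-ratio criterion.** At p0 = 14.7%:
- GS010 versus placebo for response at 0.8: odds 0.1723 × 0.8 = 0.1379, a GS010 rate of 12.1%, which is harm.
- The ratio inverted (placebo versus GS010, or non-response as the event): 0.8 corresponds to 1/0.8 = 1.25 for GS010, odds 0.2154, a rate of 17.7%, which is benefit.

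**The case against.** The strongest reply is that `ARM` is defined as the subject's arm, so the pooled model validly compares bilaterally with unilaterally treated subjects, as the SAP does for quality of life. That is true, and it makes the fault one of labelling and interpretation. However, the levels are named GS010 and Placebo, the model is described as eye-level with an eye factor, and 13.1.5 shows that the authors separate the cells when they want eye-level contrasts. It is also fair that the bias runs toward no effect and that SAP 6.3 puts all alpha on the primary endpoint.

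A reader might go further in four ways that the documents do not support:
- **That the responder analyses as a whole are wrong.** The separate second-eye model is a valid randomised contrast. The first-eye model compares GS010 with GS010 across arms and is only mislabelled.
- **That the 0.8 criterion flags harm.** It does so only if read as GS010 versus placebo for response. The protocol states neither the numerator arm nor the event, and the SAP code states neither the modelled level of `resp` nor a reference level for `ARM`. What can be shown is an undefined direction.
- **That stabilised must mean below 0.30.** Two of the three statements, including the operational formula, include +0.30.
- **That many eyes sit on that boundary.** The documents give no frequency of CF-to-HM change.

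**Conclusion.** The point holds for the pooled two-eye model. Half of its placebo-labelled eyes received GS010, the code departs from its own text, and the odds ratio cannot be read as an eye-level treatment effect. Under the stated assumptions a true odds ratio of 2 appears as about 1.36 to 1.41 in closed form, or 1.34 to 1.48 in the simulated mixed model. The size rests on assumed response rates (only 14.7% is documented), assumed random-intercept SDs, no baseline covariate, and no influence of one eye's treatment on the other. The direction follows from the coding when first-eye response does not differ between arms.

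The contradiction at +0.30 and the undirected 0.8 criterion are also established, as matters of definition. The second-eye logistic model and the primary ANCOVA are unaffected by the miscoding, and the sample size stands. Because these are secondary analyses without alpha control, this should be corrected but is not a must-fix.

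**What to change.** 1. In the pooled model, replace `ARM` by the per-eye treatment cell (`TREAT`, as in SAP 13.1.5). Report two contrasts: second-eye GS010 versus placebo, and first-eye bilateral versus unilateral. Bring text and code into agreement, and relabel the first-eye logistic model as bilateral versus unilateral.
2. Choose one stabilised boundary and use it in the words, letters and formula of both documents. The formula and the letters already agree on a change of at most 0.30. Round LogMAR change to two decimals before applying any threshold.
3. State the modelled event and the reference level explicitly in the logistic code. Restate the protocol criterion as an odds ratio above 1.25 (GS010 versus placebo, response), or record its removal in SAP 3.4.

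The cost is wording and code. No data collection, sample size or primary analysis changes. Counts of gainer and stabilised eyes may shift for eyes exactly on a threshold.
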